9.4. Concomitant Medications

During the screening process, information regarding concomitant medications, such as diazoxide or octreotide, prescribed by the referring physician must be documented. Medications taken within 4 weeks of Screening will be documented on the concomitant medication log. Any changes to a subject’s concomitant medication regimen during the study will also be documented on the concomitant medication log.

10. STUDY PROCEDURES

10.1. Screening Visit

Subjects will be screened to confirm they meet the selection criteria for the study. The investigator or study team member will obtain informed consent from each subject's parent/guardian in accordance with the procedures described below (see Section 16.3).

All subjects will be in-patients. Those less than 1 month of age or with unstable condition will be in the neonatal intensive care unit. As such, vital signs will be monitored continuously via cardiorespiratory monitoring. All enteric feedings will consist of FDA-approved, hospital-issued infant formula or breast milk provided by the mothers.

Subjects will undergo the following procedures to confirm they meet eligibility criteria for this study:

- Review medical history and medications
- Length and weight
- Blood pressure and pulse
- Physical examination
- Venous blood draws for tests as outlined in the Schedule of Activities (Table 5)
- Assessment of inclusion/exclusion criteria by Study investigator

10.2. Treatment and Evaluation Phase

Subsequent to qualification for the study and receipt of parental consent, the following procedures will be completed:

10.2.1. Period 1: Baseline GIR (Day -1)

During this baseline phase, IV glucagon, octreotide and diazoxide will be safely withdrawn prior to randomization of study drug on Day 0. Continuous "basal" enteric feed will be held constant during all study periods unless GIR=0. Subjects will consume meals as needed and GIR will be adjusted to achieve glucose minimally above 70 mg/dL.

Determine minimal GIR required to keep glucose >70mg/dL, by weaning the IV glucose Q3H pre-feeds (or Q3H if on continuous feeds). During all study periods, point-of-care (POC) blood glucose will be monitored by each site's standard practice, which will involve use of the Nova StatStrip® Hospital Glucose Measuring System, ACCU-CHEK Inform II, or an equivalent system. At the discretion of the PI, the CGM specified for Period 2 (see 10.2.2) may be placed during Period 1. As per standard care practices, blood glucose will be checked every 3 hours at a minimum, or more frequently at the discretion of the PI as the clinical situation dictates.

- Wean IV fluids as follows:
 - a. if POC glucose is >70 mg/dL (3.3 mmol/L) and < 90 mg/dL(5 mmol/L), reduce the GIR 1 mg/kg/min and check blood glucose in 3 hours.

- b. if POC glucose is >90 mg/dL (5 mmol/L) and <120 mg/dL (6.7 mmol/L), reduce the GIR by 2 mg/kg/min and check blood glucose in 1 hour.
- c. if POC glucose is >120 mg/dL (6.7 mmol/L), reduce GIR by 3 mg/kg/min and check blood glucose in 1 hour.

Note: the intent of the weaning procedure is to achieve minimal GIR at which POC glucose drops just below 70 mg/dL. Once POC glucose < 70 mg/dL has been achieved at least twice, the subject can transition to Period 2. If operational considerations preclude an immediate transition, the GIR will be returned to the previous “safe” level that maintained POC glucose > 70 mg/dL until the subject can be randomized. The “baseline” GIR will be the average GIR during the weaning procedure, minus the first two hours, and excluding the post-weaning period of “safe” GIR, if applicable.

- If GIR cannot be reduced because glucose level is <70 mg/dL (3.9 mmol/L), increase GIR by 2 mg/kg/min and check blood glucose in 1 hour.
- If glucose is <50 mg/dL (2.8 mmol/L), give 200 mg/kg dextrose by IV push, increase GIR by 2 mg/kg/min, and check blood glucose in 30 minutes.

The identified GIR must be achieved twice within $\pm 20\%$ during before proceeding to period 2.

More frequent or smaller GIR changes may be done at the investigator’s discretion should the clinical condition so require.

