More frequent, or smaller, GIR changes may be done at the investigator’s discretion should the clinical condition so require.

The average of the GIR levels after the initial 2 hours will be considered as the baseline GIR. Should time of day scheduling make transition to the randomized period 2 difficult, the investigator has discretion to keep the subject at a “safe” GIR, which is higher than the minimal rate determined during weaning, until transition to period 2 can be achieved without risk of protocol deviations. The identified baseline GIR must be achieved twice within $\pm 20\%$ before proceeding to period 2.

Period 2. Randomized Treatment

Day 0:

- Insert CGMS (Dexcom® G4 Platinum) and calibrate per manufacturer. The CGM will be used for rapid alerts, which will trigger POC assessments of blood glucose that will be used to guide clinical decisions. At the investigator's discretion, this may be inserted during Period 1.
- Obtain randomization and OmniPod® containing randomized treatment.
- When CGM has stabilized (minimally 2 hours) and is reporting glucose values, draw blood for plasma insulin and glucagon levels and immunogenicity testing prior to application of the OmniPod® pump.
- Photograph the site of approximate cannula insertion prior to application of the patch pump.
- Using the appropriate syringe (see Section 9.3.3), the treatment dispenser should load a fresh OmniPod® pump with 1 mL CSI-Glucagon™ solution (5 mg/mL concentration) or placebo as per the randomization scheme, and provide the loaded pump to study staff.
- Study staff will weigh the loaded pump to the nearest whole mg (see Appendix 2), and then apply the OmniPod® pump containing CSI-Glucagon™ solution or placebo to the abdomen of the subject (see Section 9.1).
- Use the PDM to instruct the pump to insert the cannula and ensure deployment as follows:
 - Listen for an audible “click.”
 - Confirm pink slide insert has moved into the window on the surface of the pump, indicating deployment.
 - Use the clear window on one end of the pump to view the inserted cannula.
- Once cannula deployment is confirmed, set basal rate at 5 µg/kg/hr (t=0).
- Monitor POC glucose every hour for the first three hours after study drug start and every 3 hours thereafter; or more frequently if the CGM shows glucose trending towards <70 mg/dL (3.9mmol/L) or >200 mg/dL (11.1mmol/L).
- Adjust IV fluids as per period 1 with the following additions:

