 - Every 7 days during treatment, dosing will be adjusted as applicable based on current subject body weight.
 - Every 2 weeks during treatment, draw a 1 mL blood sample for immunogenicity testing.
 - Each time study treatment is paused, and when treatment ends, draw blood for immunogenicity testing, plasma glucagon and insulin levels as well as CBC and CMP, resume IV fluids at pre-study rate and then manage glucose as per standard procedures.
- Period 4, Post-treatment Immunogenicity Testing**
- At 28 ±14 days after the last dose of study drug, the subject should have blood drawn for immunogenicity testing. This blood draw can be done at a local hospital, laboratory or clinic, or by home health care professional if subject is not able to return to the clinical site due to travel considerations.

Bio-statistical Considerations: For each subject, the average GIR will be computed for periods 1 (baseline) and 2 (treatment) by determining the area under the curve of GIR excluding the first 2 hours versus time and then dividing by the time duration for each of the periods excluding the first 2 hours, using the last 24 hours for each period, or if less than 24 hours is available, the available data, excluding the first 2 hours. The primary comparison of treatment and placebo will be based on a success-failure determination (see Section 5.1). The primary comparison will be based on the observed treatment and placebo failure rates, using subjects having enough information from periods 1 and 2 to determine success or failure.

This is a parallel group adaptive design with one interim analysis after 6 subjects in each study arm have completed their success-failure determination. If, at the interim analysis, the observed treatment failure rate

is lower than placebo so that the one-tailed p value is less than or equal to 0.0124 (Fisher's exact test, hypergeometric distribution based on the total number of observed failures) then the study will be stopped due to early demonstration of treatment efficacy.

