8.3. Randomization Criteria

Randomization will occur at the end of period 1 of the study through a centralized web-based system. Subjects will be randomized until the requirements of the interim analysis are achieved (see Section [13.4](#)), at which point randomization will be halted, pending the outcome of the analysis.

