13.2.1. Primary Endpoint (Pharmacodynamic)

For each subject, the average GIR will be computed for periods 1 (baseline), 2 (treatment) by determining the area under the curve of GIR excluding the first 2 hours versus time and then dividing by the time duration for each of the periods excluding the first 2 hours using the last 24 hours for each period, or if less than 24 hours is available, the available data excluding the first 2 hours.

The primary comparison of treatment and placebo will be based on a success-failure determination (see Section 5.1).

This is a parallel group, adaptive design with one interim analysis after 6 subjects in each study arm have completed their success-failure determination. If, at the interim analysis, the observed

treatment failure rate is lower than placebo so that the one-tailed p value is less than or equal to 0.0124 (Fisher's exact test, hypergeometric distribution based on the total number of failures) then the study will be stopped due to early treatment efficacy.

If this interim one-tailed p value is greater than 0.0124 but less than or equal to 0.05, then the study will continue and an additional 3 more subjects per study arm will be randomized. If this interim one-tailed p value exceeds 0.05 then the study will continue, and an additional 6 more subjects will be randomized. The final analysis will be based on the observed treatment and placebo failure rates using all subjects with a success-failure determination. If, at the final analysis, the observed treatment failure rate is lower than placebo so that the one-tailed p value is less than or equal to 0.04 (hypergeometric distribution) then treatment efficacy will be established.

The actual type 1 errors are smaller than the efficacy criteria would suggest because of the small sample sizes and the use of Fisher's exact test. From Monte-Carlo simulations the overall type 1 error for this design is bounded above by 0.016 for null hypothesis treatment = placebo failure rates at any failure rate using the above criteria. The type 1 error achieves its maximum at treatment = placebo = 0.5, and for this design the maximum is 0.016 as estimated by 10,000 Monte Carlo replications of the design.

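### Baseline GIR, the denominator of the primary endpoint, is defined differently in Section 10.2.1 and in Section 13.2.1 and the Synopsis, and the difference can reverse a success or failure call

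*Combined protocol and SAP*

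**What the plan says.** Section 5.1 defines treatment failure by the percentage reduction in GIR from a baseline determined before randomization. It does not say how that baseline is averaged. Other parts of the combined protocol and SAP do, in three wordings:

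- **Section 10.2.1 (Period 1):** baseline "GIR will be the average GIR during the weaning procedure, minus the first two hours, and excluding the post-weaning period of" safe GIR. There is no 24 h window.
- **Section 13.2.1 (primary endpoint):** the average for each period is an area under the GIR curve divided by time, "using the last 24 hours for each period, or if less than 24 hours is available, the available data excluding the first 2 hours". The Synopsis, under Bio-statistical Considerations, repeats this: "using the last 24 hours for each period, or if less than 24 hours is available, the available data, excluding the first 2 hours". Neither excludes the safe hold.
- **Synopsis, Period 1:** "The average of the GIR levels after the initial 2 hours will be considered as the baseline GIR". This gives neither the window nor the exclusion.

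The hold is provided for in two places. In Section 10.2.1, an infant who cannot move on at once goes back to the rate called safe, a "level that maintained POC glucose > 70 mg/dL until the subject can be randomized". The Synopsis allows it with the words "Should time of day scheduling make transition to the randomized period 2 difficult". Section 8.3 places randomization at the close of Period 1: "Randomization will occur at the end of period 1 of the study through a centralized web-based system".

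Baseline GIR is also used in the minimization (Section 9.1) and in the 12 h and 24 h checks (Section 10.2.2). The 24 h check decides which infants move early to open label (Section 10.2.3).

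**The concern.** The hold ends at randomization and randomization ends Period 1, so the hold is the last part of Period 1. Section 10.2.1 removes it from baseline; Section 13.2.1, read as written, keeps it. The two sections also use different windows, so a long wean separates them even without a hold. No text sets precedence.

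Three things are at stake.

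1. The same infant can be a success under one definition and a failure under the other.
2. If the site uses one baseline at 24 h and the analysis uses the other, an infant moved to open label as a failure can pass the 24 h criterion in the analysis and yet have no blinded 48 h data. Section 5.1 has no rule for that infant, and Section 13.2.1 bases the final analysis on subjects with a success-failure determination.
3. The interim look has 6 infants per arm, so a single changed call can matter.

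**Working it through.** **The plan's own figures.** Exact enumeration of the two-stage design gives early power 65.9% (stated 66%) and overall power 99.0% (stated over 98%) at failure rates 0.9 v 0.1, and early power 88.2% (stated 88%) at 0.95 v 0.05. These reproduce. They take the failure rates as given, so the baseline question does not alter them.

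**Formulas.** Let W be the wean length in hours, h the hold, and T = W + h.

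- Section 10.2.1: mean GIR over hours 2 to W.
- Section 13.2.1: mean GIR over hours max(2, T − 24) to T.
- They are identical when h = 0 and T ≤ 26.

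**Inputs.** The thresholds are from Section 5.1 and the GIR steps from Section 10.2.1 (including +2 after a low reading, two readings below 70 mg/dL, then a return to the previous safe level). The documents give no wean profiles or hold lengths, so those below are assumptions. GIR is in mg/kg/min.

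**Profile (a).** 14 down to 9 by 1 every 3 h, then 11 for 1 h, 10 for 3 h, 9 for 3 h (W = 25), then hold at 10.

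- Section 10.2.1: (14×1 + 3×(13+12+11+10+9) + 11 + 30 + 27)/23 = 247/23 = 10.74.
- Section 13.2.1, 12 h hold: (20 + 27 + 11 + 30 + 27 + 120)/24 = 235/24 = 9.79. With 6 h: 242/24 = 10.08. With 2 h: 253/24 = 10.54.

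**Profile (b).** 10 for 3 h, 8 for 1 h, 10 for 1 h, 8 for 1 h (W = 6), then hold at 10.

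- Section 10.2.1: 36/4 = 9.00. Section 13.2.1, 12 h hold: (36 + 120)/16 = 9.75.

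**Profile (c).** 12 down to 9 by 1 every 3 h, then the same final steps as (a) (W = 19), then hold at 10.

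- Section 10.2.1: 170/17 = 10.00. Section 13.2.1: 240/24 = 10.00 with a 7 h hold; 235/24 = 9.79 with 12 h.

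| Profile, hold | 10.2.1 | 13.2.1 | On-treatment GIR | Reduction, 10.2.1 | Reduction, 13.2.1 | Call |
|---|---|---|---|---|---|---|
| (a), 0 h | 10.74 | 10.74 | 7.0 | 34.8% | 34.8% | same at 33% |
| (a), 2 h | 10.74 | 10.54 | 7.0 | 34.8% | 33.6% | same at 33% |
| (a), 6 h | 10.74 | 10.08 | 7.0 | 34.8% | 30.6% | differs at 33% |
| (a), 12 h | 10.74 | 9.79 | 7.0 | 34.8% | 28.5% | differs at 33% |
| (b), 12 h | 9.00 | 9.75 | 7.5 | 16.7% | 23.1% | differs at 20% |
| (c), 12 h | 10.00 | 9.79 | 7.0 | 30.0% | 28.5% | same at 33% |

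**Shortest hold that changes the call.** In (a) the Section 13.2.1 baseline must fall to 7.0/0.67 = 10.448. Solving (253 − 3(h − 2))/24 = 10.448 gives h = 2.75 h. In (b) it must reach 7.5/0.80 = 9.375. Solving (36 + 10h)/(4 + h) = 9.375 gives h = 2.4 h.

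**Long wean, no hold.** 18 down to 12 by 1 every 3 h, then 14 for 1 h, 13 for 3 h, 12 for 3 h (W = 28): 368/26 = 14.15 under Section 10.2.1 and 333/24 = 13.88 under Section 13.2.1.

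**How narrow the effect is.** In (a) with a 12 h hold, the calls differ only for on-treatment GIR between 0.67×9.79 = 6.56 and 0.67×10.74 = 7.20 (33% criterion), or between 0.80×9.79 = 7.83 and 0.80×10.74 = 8.59 (20% criterion). Section 6.4.2 reports a mean reduction of roughly 50% with IV glucagon. An on-treatment GIR of 5.0 is a success either way: 53.4% v 48.9% in (a), and 44.4% v 48.7% in (b) with a 12 h hold.

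**Interim decision, 6 per arm.** With 6 placebo failures and k treatment failures, one-sided Fisher p = C(6,k)/C(12,6+k): k = 0, 1/924 = 0.0011; k = 1, 6/792 = 0.0076; k = 2, 15/495 = 0.0303. Against the 0.0124 boundary, moving from k = 1 to k = 2 changes stopping into continuing with 3 more per arm. Moving from k = 0 to k = 1 changes nothing.

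**The case against.** The best defence is that the specific rule governs the general one. Section 10.2.1 is the procedural section that defines baseline by name, and Section 10.2.2 compares against the value determined in Period 1, so sites would naturally use it. The sentence in Section 13.2.1 can be read as a general averaging recipe for both periods, with the success-failure rule taken from Section 5.1. This is a fair account of what sites would do. It does not settle the analysis: Section 13.2.1 is itself the derivation of the primary endpoint, and no text subordinates it to Section 10.2.1.

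Second, the size is assumed. The on-treatment values were chosen near a threshold, one profile does not flip, and profile (a) with a 12 h hold runs 37 h although Period 1 is labelled Day -1. This stands as a limit on what can be claimed about frequency. It does not remove the possibility: profile (b) flips after 6 + 2.4 = 8.4 h in total, and no maximum hold is stated.

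Third, baseline is fixed before randomization and the shift can go either way, so no bias between arms is shown. That is right. The Fisher illustration also applies to any reclassified infant, whatever the cause. Section 13.4 leaves interim analysis details to a DSMB charter that is not among the documents, and the charter might settle the point for the interim.

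Fourth, changing the baseline used at 24 h could alter which infants near the threshold move to open label. That bears on how the fix is worded.

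**Conclusion.** The concern holds. Following Section 13.2.1 as written produces a baseline that Section 10.2.1 rules out whenever there is a safe hold, and the two windows differ whenever the wean runs beyond 26 h. This is a contradiction in the denominator of the primary endpoint, not a missing detail.

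The practical size is limited. With assumed 12 h holds, the two definitions differ by 0.95 in profile (a) (10.74 − 9.79), by 0.75 in the opposite direction in (b) (9.75 − 9.00) and by 0.21 in (c) (10.00 − 9.79). Only infants near the 20% or 33% threshold change category, and the documents give no data from which to estimate how many. No type 1 error inflation, loss of the stated power or bias between arms is claimed. The text conflict is certain; its numerical effect rests on the assumed profiles. It should be corrected before unblinding because the sample is small and the choice should not be made with results in view.

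**What to change.** Before unblinding, write one analysis definition of baseline GIR and use it in Section 5.1, Section 10.2.1, Section 13.2.1 and both places in the Synopsis. It should state a single averaging window and carry the Section 10.2.1 exclusion of the safe hold into Section 13.2.1 and the Synopsis. Reconcile the baseline referred to in the minimization (Section 9.1) and in the 12 h and 24 h checks (Section 10.2.2) with that definition, without changing any weaning, pump or switching rule. Keeping the Section 10.2.1 window would leave unchanged the baseline for sites that already follow that section; any other window would need this point addressed explicitly.

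Optionally, add one sensitivity table that re-derives success and failure under the alternative definition.

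The cost is wording in the protocol, Synopsis and statistical section, plus that table if wanted. GIR by time is already needed for the area-under-the-curve average, so no new data are required.

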10.2.2. Period 2: Blinded, Randomized Treatment (Days 0-1)

Once baseline GIR has been established in Period 1, the following procedures will be completed, including initiation of blinded study treatment.

Day 0

1. If not inserted during Period 1, insert CGM (Dexcom® G4 Platinum) and calibrate per manufacturer. Stabilize for a minimum of 2 hours and confirm CGM is reporting glucose values before proceeding to step 2.
{Note: The CGM will be used for rapid alerts, which will trigger POC assessments of blood glucose that will be used to guide clinical decisions.}
2. Draw blood for plasma insulin and glucagon levels and immunogenicity testing (as listed in [Table 5](#)), prior to application of the OmniPod® pump.
3. Photograph the site of approximate cannula insertion prior to application of the OmniPod® pump.
4. Using the appropriate syringe (see [Section 9.3.3](#)), load a fresh OmniPod® pump with 1 mL CSI-Glucagon™ solution (5 mg/mL concentration) or placebo as per the randomization scheme.
5. Study staff will weigh the loaded pump to the nearest whole mg (see [Appendix 2](#)), and then apply the OmniPod® pump to the abdomen of the subject (see [Section 9.1](#)).
6. Use the PDM to instruct the pump to insert the cannula and ensure deployment as follows:

- Listen for an audible “click.”
 - Confirm pink slide insert has moved into the window on the surface of the pump, indicating deployment.
 - Use the clear window on one end of the pump to view the inserted cannula.
7. Once cannula deployment is confirmed, set basal rate at 5 µg/kg/hr. Record time of starting the pump; this is t=0.
 8. Monitor POC glucose every hour for the first three hours after study drug start and every 3 hours thereafter; or more frequently if the CGM shows glucose falling <70 mg/dL (3.9 mmol/L) or rising above >200 mg/dL (11.1 mmol/L). Additionally, the trajectory of change in plasma glucose concentration based on the two most recent POC measurements should be used to adjust the frequency of glucose monitoring as needed to prevent plasma glucose <70 mg/dL (3.9 mmol/L) or >200 mg/dL (11.1 mmol/L).
 9. Adjust IV fluids as per period 1 with the following additions:
 - a. If POC glucose is >70 mg/dL (3.9 mmol/L) and GIR=0, introduce and/or extend the fasting period after meal feeding as long as possible, while maintaining POC glucose > 70 mg/dL.
 - b. If GIR cannot be reduced because glucose level is < 70 mg/dL (3.9 mmol/L), **restore continuous enteric feeding if that has been suspended**, or increase glucose infusion rate by 2 mg/kg/min and **increase study drug infusion rate by 5 µg/kg/hour (to a maximum of 20 µg/kg/hr)** and check blood glucose in 1 hour.
 10. If glucose is <50 mg/dL (2.8 mmol/L), give 200 mg/kg dextrose by IV push, increase GIR by 2 mg/kg/min, **increase study drug infusion rate by 5 µg/kg/hour (to a maximum of 20 µg/kg/hr)** and check blood glucose in 30 minutes. At 12 hours after start of study drug, determine average GIR since the start of blinded therapy, excluding the first 2 hours. If average “on treatment” GIR has been reduced by < 20% from the baseline value determined in Period 1, take the following actions:
 - a. Remove the pump and weigh it.
 - b. Replace the pump with a new one at the same flow rate setting as the previous pump and a fresh supply of the same blinded study drug.
 - c. Monitor POC glucose over the next 12 hours, adjusting GIR using the same rules as above for making IV fluid adjustments in the interim.

{Note: This same procedure should be followed if the pump alarms or if there is an acute deterioration in an otherwise stable subject, indicating a possible occlusion.}

Day 1

At 24 hours after the initial start of study drug, determine average GIR since the start of blinded therapy, excluding the first 2 hours. Then compare the “on treatment” GIR to the baseline value determined in Period 1 and calculate the percentage change. Depending on percentage change in GIR, follow the procedures under either item 1 or item 2.

1. At 24 hours if average GIR has been reduced by < 20% from the baseline value determined in Period 1, complete the following procedures:

- a. Draw blood for plasma insulin and glucagon levels as well as CBC and CMP.
 - b. Remove and weigh the OmniPod® pump (Appendix 2) and:
 - a. Photograph the application site, paying particular attention to the cannula insertion site.
 - o Assess site for edema and erythema using the Draize scale. Any Draize scores >0 should be followed to resolution, including a follow-up photograph.
 - c. Proceed to Period 3 (see 10.2.3).
2. At 24 hours if average GIR has been reduced by $\geq 20\%$ from the baseline value determined in Period 1, complete the following procedures:
- a. Continue to adjust the GIR during day 1 as per day 0.
If GIR=0, continuous enteric feeding has been completely weaned, and plasma glucose continues to rise, reduce study drug infusion rate by 2.5 $\mu\text{g}/\text{kg}/\text{hr}$ every 6 hours to a minimum of 2.5 $\mu\text{g}/\text{kg}/\text{hr}$, as long as the pre-meal blood glucose is >70 mg/dL (3.9 mmol/L).

At approximately 48 hours from the start of the first blinded study treatment, complete the following:
 - b. Draw blood for insulin and glucagon levels as well as CBC and CMP.
 - c. Remove the OmniPod® pump, weigh it, and photograph the application site, paying particular attention to the cannula insertion site.
 - d. Assess site for edema and erythema using the Draize scale. Any Draize scores > 0 should be followed to resolution, including a follow-up photograph.
 - e. Proceed to Period 3 (see 10.2.3).

